Study Protocol

Restoration of the Fecal Microbiome after Antimicrobial Exposure with Autologous Fecal Flora Restoration Therapy

Date: December 11, 2014

ClinicalTrials.gov ID: 201312022

Methods

Hypothesis: Autologous fecal microbiota therapy (auto FMT) will be able to rapidly, and safely, restore a patient's fecal microbiome after antimicrobial exposure.

[figure not shown]
Specific Aims:

1. Determine the effects five days of amoxicillin/clavulanic acid on the fecal and urinary microbiomes of healthy volunteers.
2. Determine whether an infusion of fecal filtrate collected prior to the antimicrobial exposure is capable of rapid restoration of a healthy fecal microbiome when infused after a course of antimicrobials.

Patient Population: Ten healthy volunteers will be recruited to participate through the Washington University Research Participant Registry (see Resources). Inclusion criteria will be healthy adults 21 to 70 years of age. Exclusion criteria will include a history of allergic reaction to beta-lactam antimicrobials; any non-topical antimicrobial exposure or tube feeds as a primary source of nutrition in the past six months; pregnant or risk of becoming pregnant during the study period; gastroenteritis in the last 3 months; any non-elective hospitalization in the previous 12 months incontinent of stool; prior resection or alteration of the stomach; small bowel, or colon; unwillingness to receive an enema/FMT; known colonization with an MDRO; anticipated change in diet or medications, or elective surgery, during the study period; positive HIV test; evidence of chronic medical conditions seen during physical exam; or a history of an intestinal disorder.

Study Procedure After written informed consent is obtained, a full physical exam including vital signs, β HCG pregnancy test in women of childbearing age, and an HIV 1/2 antibody test will be performed. The subject will be provided with a sealable stool collection device. The subject will be instructed to bring back stool and urine specimens at their convenience within the next week, preferably within two hours after the bowel movement/urination. If the bowel movement has been at room temperature for greater than 6 hours, the subject will be asked to bring back another stool specimen. In case the subject has a bowel movement after hours or is unable to deliver the specimen within two hours, the subject will be instructed to contact a pre-identified courier to pick up the urine and stool specimens. Please see below on how stool and urine will be processed for microbiome interrogation (stool and urine specimens) and FMT (autologous FMT). After the first stool specimen is collected, the subject will be provided with a five day supply of amoxicillin/clavulanic acid.

Figure Study procedure overview. 10 patients will be enrolled. Half will be randomized to FMT and the other half will receive saline enemas. Stool will be collected at enrollment, after the course of antimicrobials, the first bowel movement after FMT/saline, and days 7, 30, and 90 after FMT. The stool specimens and FMT product will be interrogated with DNA-based microbiome methods and semi-quantitative culture

Explicit directions on how to take amoxicillin/clavulanic acid will be provided, as well as instructions to bring the pill bottle back to confirm all doses were taken. A return visit will be scheduled one or two days after amoxicillin/clavulanic acid is to be completed. The subject will be instructed to provide stool specimens after

amoxicillin/clavulanic acid has been completed but before FMT/saline. The subject will be able to bring the specimens with them to the FMT/saline visit if they are less than two hours old, or drop off/courier specimens prior to the appointment. The FMT/saline will be administered by enema in the outpatient setting by trained research personnel. The subject will be instructed to collect the first bowel movement after FMT/saline (immediate release of enema material will be excluded), as well as urine at that time, and also bowel movements at day 7 ± 2 , day 30 ± 2 , and day 90 ± 2 . The subject will be supplied with all necessary materials for stool collection and drop-off at each stool collection time point.

Data Management: Demographic data, including age, gender, race/ethnicity, height, weight, comorbidities, and tobacco and alcohol history, will be obtained on enrollment. All medications the subject received in the 6 months prior to first stool/urine collection will be recorded. The subject will be provided a questionnaire on bowel movement consistency (per Bristol stool chart) and frequency, diet in past week, and medications taken to be completed at time of enrollment, FMT/saline, and all subsequent stool/urine collection time points.

Stool specimens: Stool specimens will be collected as cited above. Fresh stool specimens will be cultured on to Brucella blood, Laked blood kanamycin vancomycin (LKV), PEA, Bacteroides Bile Esculin (BBE), MacConkey, Hectoen Enteric, Campylobacter blood, blood, Colistin-Naladixic, and cycloserine cefoxitin fructose (CCFA) agars semiquantitatively to assess viability of aerobic and anaerobic gram positive and gram negative organisms. DNA will be extracted prior to freezing, or processing of the pre-antimicrobial specimen, of residual stool using the MOBIO PowerSoil kit, as performed for the NIH Human Microbiome Project at Washington University (60;62). Parallel sequence datasets will be generated for each of the samples at the Genome Institute at Washington University as previously described for the HMP (58-60). This will involve 1) PCR amplification of bacterial rRNA genes using degenerate primers to capture rRNA genes from a broad diversity of bacteria, followed by sequencing of two separate segments of the 16S rRNA gene encoding either the V1 through V3 (V1-V3) or V3 through V5 (V3-V5) hypervariable regions on the 454 sequencing platform. Of note, the 454 sequencing primers used in this current study will be identical to the primers employed for characterizing the microbial communities in healthy individuals at different body sites, including the gastrointestinal tract by the Human Microbiome Project. All sequences will be processed as in the HMP to remove artifactual chimeric sequences and regions of low sequence quality, and then only sequences greater than a certain length (usually 200 bases) will be used for further analysis. Analyses will be performed by the methods used for previous studies at the Genome Institute (58;60;61) and will include quantitative statistical techniques to compare microbial community composition (taxa that are present) and structure (abundance of taxa). Where differences are found, it is usually possible to specify which species are most at variance between samples, and thus pinpoint potentially technical problems to be addressed in the preparation and re-establishment of fecal microbiomes. We also note that this methodology will allow us to initially classify the subjects as to which enterotype (63;64) their microbiome belongs to, in case this is a variable that would require stratification in application of the method.

We will also perform shotgun sequencing on a subset of the samples (the pre-antimicrobial sample, the enusate, and the final 90 day sample). Shotgun sequencing allows for detection of non-bacterial entities such as viruses (50) and eukaryotic microbes, as well as detection of bacterial virulence factors, antibiotic resistance genes, and other relevant elements. Analyses will be as performed in the references cited above for the HMP in order to determine if these factors pose problems for the process.

Autologous FMT: The pre-antimicrobial stool specimen will be processed for FMT within two hours of collection. Approximately 150 gm of stool will be homogenized with 250ml of non-bacteriostatic saline. The slurry will be passed through stainless steel strainers to remove particulate matter. Sterile pharmaceutical grade glycerol will be added to a final concentration of 10%, and the specimen will be frozen at -80°C (43). After the antimicrobials have been discontinued and the patient has provided a post-antimicrobial bowel movement, the enema material will be thawed over 2 to 4 hours in an ice bath for the patient undergoing autologous fecal flora restoration therapy. A 10 ml aliquot of the material will be saved for viability count

cultures and microbiome interrogation per above. The remaining material will be administered to the patient by enema, and the patient will be instructed to retain the material for as long as possible. A 10 ml aliquot of the non-bacteriostatic saline enema given to patients undergoing the sham procedure will also be collected for viability count cultures and microbiome interrogation as well.

Analysis: As mentioned above, analyses will be performed by the methods used for previous studies at the Genome Institute (58;60) and will include quantitative statistical techniques to compare microbial community composition (taxa that are present) and structure (abundance of taxa). Most methods are performed using functions in the R package, and include calculation of proximity measures such as Bray-Curtis index, comparison of communities using hierarchical clustering, multidimensional scaling, and/or Principal Component/Coordinate Analysis. The Genome Institute has recently developed additional metrics for community comparison using a tree-based approach (65). It is usually possible to specify which species are most at variance between samples, and thus pinpoint potentially technical problems to be addressed in the preparation and re-establishment of fecal microbiomes. Enterotype (63;64) analysis will also be performed on the initial subjects to determine if there is any correlation between this parameter and outcome.

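### Do the six-hour replacement rule and the two-hour FMT processing limit for the first stool contradict each other?

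*Combined protocol and SAP*

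**What the plan says.** Study Procedure asks the volunteer to return stool and urine "at their convenience within the next week". The delivery target is worded "preferably within two hours after the bowel movement/urination". Two-hour delivery is thus a preference. Transport is arranged for stools passed outside working hours and for volunteers who cannot come in time: "unable to deliver the specimen within two hours, the subject will be instructed to contact a pre-identified courier". The only stated ground for requesting another stool is "If the bowel movement has been at room temperature for greater than 6 hours". The next step is timed as follows: "After the first stool specimen is collected, the subject will be provided with a five day supply of amoxicillin/clavulanic acid".

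The Autologous FMT section sets a firmer limit for the same stool: "The pre-antimicrobial stool specimen will be processed for FMT within two hours of collection". Neither section defines collection, and neither says what is done with a first stool that misses this limit.

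**The concern.** The two sections appear to apply different clocks to one specimen. If collection means the bowel movement, a stool that arrives four hours old is not replaced under Study Procedure, yet it has already missed the Autologous FMT limit. Some of the plan's wording supports that reading: "The subject will be provided with a sealable stool collection device", and later "The subject will be instructed to collect the first bowel movement after FMT/saline", so collecting is something the volunteer does. The supplies sentence also lists collection separately from drop-off.

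The possible loss is irreversible for a given volunteer. The first stool is the source of the infusion tested under the second Specific Aim, and no pre-antibiotic stool can be obtained once the antibiotic has been started. The text places the antibiotic supply after collection and does not mention successful processing. The data items listed under Data Management include neither the time of the bowel movement nor the time of processing, so infusion viability could not later be related to stool age from those items.

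**Working it through.** The plan gives no figure to reproduce, so the check sets the limits side by side under each meaning of collection.

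**Inputs**
- Replacement trigger: more than 6 h at room temperature (Study Procedure).
- Preferred delivery: 2 h after the bowel movement (Study Procedure).
- FMT processing limit: 2 h after collection (Autologous FMT).
- Volunteers: 10, half randomised to FMT (figure caption, Study Procedure).
- Stool time points: enrolment, after the antibiotic, first bowel movement after the enema, and days 7, 30 and 90, which makes 6.

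**Age at processing under each reading**

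| Clock starts at | Result |
|---|---|
| Bowel movement | Accepted to 6 h, compliant to 2 h: 6 − 2 = 4 h of accepted age that cannot comply. Delivery at exactly 2 h leaves 2 − 2 = 0 h for processing. |
| Receipt by staff | Limits compatible. Age at processing up to 2 + 2 = 4 h for preferred delivery, and 6 + 2 = 8 h at the replacement limit. |
| Courier pick-up | Depends on pick-up and transit times, which the documents do not give. |

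The 8 h figure is not a firm bound, because the six-hour rule counts only time at room temperature. The 4 h and 8 h figures describe alternative readings and do not measure impact.

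**Specimens concerned**
- All planned stools: 6 × 10 = 60.
- First stools: 1 × 10 = 10, so 10 of 60.
- Infused: 10 / 2 = 5. One affected product would be 1/5 = 20% of the FMT arm. This is the weight of one product and says nothing about how likely the event is.

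**Order of steps before the source is lost**
1. The stool arrives. Staff must establish its age to apply the six-hour rule, so on the bowel-movement reading a stool older than two hours is recognised at receipt.
2. On either the bowel-movement or the receipt reading, it is known no later than 2 h after receipt whether the processing limit was met.
3. The antibiotic is supplied after this stool. The sentence gives an order in time and does not make collection the only condition.
4. A request for another specimen is already an established step, and the volunteer has a week in which to return one.

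For the source to be lost, a stool must miss the limit, staff must not act on an age or delay they know, the antibiotic must be started, and the volunteer must be allocated to FMT. The documents give no probability for any of these except the allocation of one half.

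**What recorded times would add.** Two clock times on ten specimens is 2 × 10 = 20 entries, so the burden is small. Viability is already measured directly, by semiquantitative culture of fresh stool and by counts on a 10 ml aliquot of the thawed enema. Relating those counts to stool age in 5 infused products could only be descriptive.

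**The case for a change.** The strongest case for a change is that the six-hour sentence is written for this very specimen: it precedes the antibiotic and leads into FMT processing. Reading six hours as a general intake limit and two hours as the FMT limit still leaves no written rule for stools in between. The courier solves transport, not a missed processing limit. The thaw-time counts come after the antibiotic course, too late to obtain a new source. Two members of staff could each follow the text and prepare infusions from stools of quite different age, in a study that wants to learn about technical problems in preparation. The repair would take a few sentences.

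Much of this is accurate: collection is undefined, the contingency is unwritten, and late viability counts cannot restore a source. The step from there to a defect is weaker. The wording that favours the bowel movement mostly concerns later stools or supplies. Where the plan wants a clock to start at the bowel movement it says so ("preferably within two hours after the bowel movement/urination"), and the Autologous FMT section does not. The sentence on antibiotic supply is the one place where collecting this first stool prompts action by staff, which fits staff having it in hand. The six-hour rule also applies to a couriered stool, so room-temperature time on that route is capped. Even on the bowel-movement reading, the narrower limit can be met by applying it to the infusion source and using the existing repeat route.

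**Conclusion.** No change to the plan follows. The two limits conflict only if the two-hour clock starts before receipt, and even then a team can satisfy both by applying the stricter limit to the stool meant for infusion. An undefined word and an unwritten contingency remain. They concern one specimen per volunteer, 10 of 60 stools and 5 infusions. Site working instructions can state which event starts the clock and what is done with a late first stool before the antibiotic is handed over. Which limit is preferable is for the investigators to decide.

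This rests on three assumptions: staff ascertain stool age at receipt, as the six-hour rule requires; they do not hand over the antibiotic while they know the source is unusable; and the one-week window leaves room for a repeat. The documents do not say how often first stools would arrive after two hours or how much viability is lost per hour. Nothing in them shows an effect on the FMT-versus-saline comparison or on any conclusion of the study.

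### No urine is scheduled between the antibiotic and the enema, so as written the urinary part of Aim 1 has no enema-free post-antibiotic sample in any of the 10 subjects

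*Combined protocol and SAP*

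**What the plan says.** Specific Aims: Aim 1 asks for the effect of five days of antibiotic on two microbiomes, fecal and urinary.

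Study Procedure sets the collections in order:

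- Baseline: "The subject will be instructed to bring back stool and urine specimens at their convenience within the next week". Stool and urine are both named.
- After the antibiotic and before the enema: "The subject will be instructed to provide stool specimens after", continuing "amoxicillin/clavulanic acid has been completed but before FMT/saline". Only stool is named.
- After the enema: the first stool is collected, "as well as urine at that time, and also bowel movements at day 7" and at days 30 and 90. Urine is named with the first stool only.

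The figure caption gives the allocation, "Half will be randomized to FMT and the other half will receive saline enemas", and a schedule that mentions stool alone: "Stool will be collected at enrollment, after the course of antimicrobials, the first bowel movement after FMT/saline", followed by days 7, 30 and 90.

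Data Management times the questionnaire "to be completed at time of enrollment, FMT/saline, and all subsequent stool/urine collection time points". This wording pairs stool with urine but does not say that urine is taken before the enema.

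**The concern.** The antibiotic effect in Aim 1 is a within-subject before/after contrast. It needs a sample before the course and one after it, with nothing else done to the subject in between. Stool has such a pair. For urine, the only clearly scheduled later sample comes after a second intervention, which is FMT in half the subjects and a saline enema in the other half. No arm goes without an enema, so no subset of subjects supplies a clean urine pair.

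The later sample is also tied to the first bowel movement after the enema. No limit is stated for that wait, so recovery time since the last dose is longer and varies between subjects. Neither problem can be repaired in the analysis, because the missing sample would never have been taken.

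**Working it through.** The document states no sample-size or power figure that bears on this point, so there is none to reproduce. The check sets every mention of urine against the collection schedule and counts subjects.

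**Inputs.** 10 subjects (Patient Population). Half to each enema type (figure caption), so 10 / 2 = 5 FMT and 5 saline. Return visit one or two days after the course is due to end (Study Procedure).

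| Time point | Stool named | Urine named | Enema already given |
|---|---|---|---|
| Baseline, before the antibiotic | yes | yes | no |
| After the antibiotic, before the enema | yes | **no** | no |
| First stool after the enema | yes | yes | yes |
| Days 7, 30 and 90 | yes | unclear | yes |

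For days 7, 30 and 90, Study Procedure names bowel movements only, while Data Management speaks of stool and urine together.

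**Enema-free baseline to post-antibiotic pairs**

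- Stool: 1 named pre-enema sample × 10 = 10 of 10.
- Urine as written: 0 × 10 = 0 of 10. The first named post-antibiotic urine follows FMT in 5 and saline in 5.
- Urine with the fix: 1 × 10 = 10 of 10.

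**Does restricting to the saline arm help?** It removes FMT but not the enema or the delay, and leaves 5 pairs. As an illustration, assume a two-sided exact Wilcoxon signed-rank test on some single-number summary of change (the document specifies no test). The smallest attainable p-value is 2 / 2^5 = 0.0625 with 5 pairs, against 2 / 2^10 = 0.002 with 10.

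**Time since the last dose, if the visit is kept as scheduled**

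- Pre-enema sample: 0 to 2 days.
- Post-enema urine: at least 1 to 2 days, plus a wait with no stated limit.

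**Urine samples under each reading of the schedule**

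- Literal (baseline and first stool after the enema): 2 × 10 = 20 now, 3 × 10 = 30 with the fix, so +10.
- Baseline and all 4 post-enema points: (1 + 4) × 10 = 50 now, 6 × 10 = 60 with the fix, so +10.
- Urine already intended at all 6 stool points: 6 × 10 = 60 before and after, so +0.

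**The case against.** The strongest reply is that this is a gap in wording and not in design. The caption omits urine even at enrollment, where it is certainly collected, so silence about urine is weak evidence. Data Management treats stool and urine as one collection, and its list can be read as making the enema visit a urine point too. The drop-off and courier arrangements for the pre-enema visit resemble those used for both specimens at baseline. The overview figure is not available in the text reviewed. The Autologous FMT section says "After the antimicrobials have been discontinued and the patient has provided a post-antimicrobial bowel movement, the enema material will be thawed" without mentioning urine, but that rule concerns preparing fecal material, so its silence carries little weight.

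Much of this stands as a reason to think urine may have been intended. None of it schedules a urine sample before the enema, however. The specimens to be brought to the visit refer back to stool, and the Data Management phrase governs the questionnaire. Urine is named explicitly in the collection instructions before and after this one, and staff following the instruction would collect stool.

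A second reply is that no harm has been shown. The baseline urine is unaffected, an enema may do little to the urinary microbiome, the first stool is plainly expected before day 7, and the randomized comparison of FMT with saline gives a small check on an FMT effect. This also stands in part: the bias could be near zero. But the randomized comparison cannot isolate what both arms share, namely an enema and a delay, and the document gives no basis for assuming that their effect is nil.

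A third reply is that an extra sample does not by itself deliver the urinary aim. Study Procedure says that urine processing is described below, yet no later section describes it, and Analysis speaks of fecal microbiomes only. That is correct and should be settled alongside this point.

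**Conclusion.** The concern holds. As written, 0 of 10 subjects have a urine sample after the antibiotic and before the enema, against 10 of 10 for stool, so the urinary half of Aim 1 is avoidably confounded with the enema and with added time. It should be fixed. Confidence is medium, because the omission may be one of wording only.

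The count rests on a literal reading of the collection instructions, without the overview figure. The figure of 10 of 10 after the fix assumes that all subjects stay in the study and give usable samples. The size of any enema effect on urine is unknown. The fix removes the enema confounding only: with no antibiotic-free arm, the before/after change still includes natural drift over the course and up to about 2 days of recovery. The fecal part of Aim 1 and Aim 2 are not affected, because a pre-enema stool is named.

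**What to change.** 1. In Study Procedure, add *and urine* to the instruction for the collection after the antibiotic and before FMT/saline. If urine was already intended there, the same edit makes it explicit.
2. List the urine time points once, including whether days 7, 30 and 90 are among them, and make Study Procedure, the figure caption and Data Management agree.
3. State that the urinary part of Aim 1 uses the baseline to pre-enema pair in all subjects. Within-subject Bray-Curtis distance, already named in Analysis for community comparison, is one option. Report it as a before/after change without an antibiotic-free comparison.
4. Supply the urine processing description that Study Procedure promises, and say that Analysis applies to urine as well as stool.

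The cost is 0 to 10 more urine samples to collect and process, depending on what was already intended. They come at a collection already scheduled, with no added visit or invasive procedure and no change to treatment.

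### The only post-antibiotic urine clearly requested for Aim 1 is taken with the first bowel movement after the enema, with no collection technique, so fecal carry-over could pass for an antibiotic effect

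*Combined protocol and SAP*

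**What the plan says.** Specific Aims, Aim 1: "Determine the effects five days of amoxicillin/clavulanic acid on the fecal and urinary microbiomes of healthy volunteers". Aim 2 and the hypothesis concern the fecal microbiome only.

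Study Procedure sets out the specimens in order:

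- **Baseline.** "The subject will be instructed to bring back stool and urine specimens at their convenience within the next week". Stool and urine are brought in together or collected together by courier.
- **After the antibiotic, before the enema.** The request names stool only: "The subject will be instructed to provide stool specimens after" the antibiotic is finished but before FMT or saline. The next sentence speaks of specimens in general that may be brought to the visit.
- **After the enema.** The subject is to collect the first stool passed following the FMT or saline enema, and the instruction continues: "immediate release of enema material will be excluded), as well as urine at that time". For days 7, 30 and 90 the same sentence names bowel movements only.
- **Materials.** "The subject will be supplied with all necessary materials for stool collection and drop-off at each stool collection time point". Nothing equivalent is said for urine.

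Data Management schedules a questionnaire at enrollment, at FMT/saline and at later time points, which it describes as being for both stool and urine.

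On handling, Study Procedure promises a description: "Please see below on how stool and urine will be processed for microbiome interrogation (stool and urine specimens". The later sections (Stool specimens, Autologous FMT, Analysis) deal with stool, the FMT product and the saline aliquot. None describes how urine is collected or processed, and none gives an analysis specific to urine.

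**The concern.** The urinary part of Aim 1 needs a urine from before the antibiotic and one from after it, with nothing else changed between them. As written, the only later urine that is plainly requested also follows an enema and is tied to a bowel movement. Antibiotic exposure and collection around an enema therefore change together.

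If stool contains far more bacteria per unit than urine (an assumption, since the protocol gives no loads), a trace of stool in the urine can shift its 16S profile noticeably. The broad-range PCR described under Stool specimens would amplify carried-over fecal DNA along with everything else. No check against the same subject's stool is planned that would reveal it. The risk is that a change in urine is credited to amoxicillin/clavulanic acid when it comes from how the specimen was obtained.

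**Working it through.** The plan gives no figure to reproduce. The check has two parts: which urines are requested, and how much carry-over could matter.

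**Which urines are requested**

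| Time | Stool | Urine | Urine technique |
|---|---|---|---|
| Baseline | requested | requested | none stated |
| After antibiotic, before enema | requested | hinted at, not plainly requested | none stated |
| First bowel movement after enema | requested | requested | none stated |
| Days 7, 30, 90 | requested | implied only by the questionnaire wording | none stated |

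No section mentions midstream or clean-catch collection, cleansing, a separate urine container, the order of void and bowel movement, or a comparison with paired stool. The exclusion of immediately released enema material defines which bowel movement is collected. It does not govern the urine.

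**How much carry-over could matter**

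All inputs here are assumptions:

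- stool load S = 1e10 to 1e11 cells per g
- urine load u = 1e3 to 1e5 cells per ml
- carried-over stool m = 0.1 or 1 microgram per ml of urine

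Fecal cells per ml of urine: c = m × 1e-6 × S. Fecal share: f = c / (c + u).

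- m = 0.1: c = 1e3 (S = 1e10) to 1e4 (S = 1e11)
- m = 1: c = 1e4 to 1e5

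| Urine load u (cells per ml) | f at 0.1 microgram per ml | f at 1 microgram per ml |
|---|---|---|
| 1e3 | 50% to 91% | 91% to 99% |
| 1e4 | 9% to 50% | 50% to 91% |
| 1e5 | 1% to 9% | 9% to 50% |

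Lowest corner: 1e3 / (1e3 + 1e5) = 0.0099, about 1%. Highest corner: 1e5 / (1e5 + 1e3) = 0.990, about 99%.

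**What that does to the planned distance measure**

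Analysis names the Bray-Curtis index. Take relative abundances, equal PCR yield per cell, a urine community that has not changed, and stool taxa that do not overlap with urine taxa.

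- Clean baseline, contaminated later urine: the distance is 1 − (1 − f) = f.
- Same stool profile carried over at both times, shares f0 and f1: the distance is |f1 − f0|. Equal carry-over then cancels.
- Equal share f at both times, but the stool itself changed by the antibiotic: the distance is f × (Bray-Curtis distance between the two stools). Equal carry-over then does not cancel, because a fecal change shows up in urine.

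The last case is why the technique matters for the baseline and pre-enema urines as well as for the post-enema one.

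**Frequency**

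The protocol gives no rate of carry-over. If 5% of the later urines were affected, the chance of at least one among ten subjects is 1 − 0.95^10 = 40%. At 30% it is 1 − 0.70^10 = 97%.

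**The case against.** Several objections have force.

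- **A pre-enema urine may be intended.** The general reference to specimens brought to the FMT/saline visit, and the questionnaire wording, can be read that way. A reader might infer that no such urine will exist, but the text does not settle that. If one is taken, Aim 1 has a post-antibiotic urine free of the enema, and only the missing technique remains. This stands, and the request needs to be made explicit.
- **Fresh soiling is not shown.** A reader might infer that the urine is passed straight after exposure to enema material. The documents do not support this. Immediate release is excluded from the collected movement, Autologous FMT asks the patient to retain the material as long as possible, and the interval is not given. Nor does the text say that the void follows the movement. Carry-over is possible, not established.
- **Baseline has the same gap.** Baseline urine also comes in with stool and has no stated technique. Greater carry-over after an enema is plausible, but nothing in the documents measures it.
- **No urinary comparison between arms is planned.** A reader might infer a false difference between FMT and saline in urine. Urine appears only in Aim 1, which is about the antibiotic, and Analysis specifies no urinary contrast by arm.
- **The size is assumed throughout.** Low bacterial density in urine is not stated in the protocol. At 0.1 microgram per ml and 1e5 urine cells per ml the share is only about 1% to 9%, so it cannot be claimed that stool would dominate the urine.
- **Technique may sit elsewhere.** A subject handout or laboratory manual, not provided here, could contain it. The missing technique is also part of a wider gap, the promised urine description that does not appear.

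These points limit the claim without removing it. The one clear instruction for a post-antibiotic urine ties it to a bowel movement after an enema, and the plan has no step that would detect contamination.

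**Conclusion.** The point holds as a minor one. The only post-antibiotic urine that the protocol plainly requests is collected with the first bowel movement after the enema, without a stated technique and without a paired-stool check. Fecal carry-over could therefore be mistaken for an antibiotic effect on the urinary microbiome.

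The fecal share of about 1% to 99% is a range over assumed loads and is not an estimate. It shows that the effect could be negligible or overwhelming and that the documents cannot say which. The conclusion rests on the protocol text alone; separate subject instructions might already cover part of it. It is confined to the urinary half of Aim 1.

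**What to change.** 1. In Study Procedure, explicitly request a urine after the antibiotic and before the enema, alongside the stool already requested then, and name it as the primary post-antibiotic urine for Aim 1. Asking only that the void precede the bowel movement at the post-enema collection is not enough, because that urine still follows the enema.
2. Use one instruction for every urine, baseline included: midstream clean-catch, after cleansing, into a separate container, before any bowel movement. Put it in the urine description that Study Procedure promises.
3. In Analysis, compare each urine with the same subject's stool from the same time and, in the FMT arm, with the infused material. Repeat the urinary comparison with stool-shared taxa removed, as a sensitivity analysis only, since some of those taxa may be genuine urinary organisms.

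**Cost.** One clearly scheduled urine within a window in which stool is already collected, a short instruction, an inexpensive kit per urine, and one added comparison using stool and infusate sequences that are already planned. Subjects have slightly more to do, and the sensitivity analysis may discard some genuine urinary taxa.
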